10.1.4 Preexisting Medical Conditions (Baseline Conditions)

A preexisting medical condition should be recorded as an AE or SAE only if the frequency, severity, or character of the condition worsens during the study. When recording such events on an Adverse Event CRF, it is important to convey the concept that the preexisting condition has changed by including applicable descriptors (e.g., “more frequent headaches”).

10.2 Grading and Reporting Adverse Events

10.2.1 Grading and Relationship to Drug

The descriptions and grading scales found in the CTEP Version 5.0 of the NCI Common Terminology Criteria for Adverse Events (CTCAE) will be utilized for AE reporting. CTEP Version 5.0 of the CTCAE is identified and located at:

http://ctep.cancer.gov/protocolDevelopment/electronic_applications/ctc.htm.

AEs not covered by specific terminology listed should be reported with common medical terminology, and documented according to the grading scales provided in the CTCAE Version 5.0.

The relationship of event to study drug will be documented by the Investigator as follows:

- **Unrelated:** The event is clearly related to other factors such as the participant’s clinical state, other therapeutic interventions or concomitant drugs administered to the participant.
- **Unlikely:** The event is doubtfully related to investigational agent(s). The event was most likely related to other factors such as the participant’s clinical state, other therapeutic interventions, or concomitant drugs.
- **Possible:** The event follows a reasonable temporal sequence from the time of drug administration, but could have been produced by other factors such as the participant’s clinical state, other therapeutic interventions or concomitant drugs.
- **Probable:** The event follows a reasonable temporal sequence from the time of drug administration, and follows a known response pattern to the study drug. The event cannot be reasonably explained by other factors such as the participant’s clinical state, therapeutic interventions or concomitant drugs.
- **Definite:** The event follows a reasonable temporal sequence from the time of drug administration, follows a known response pattern to the study drug, cannot be reasonably explained by other factors such as the participant’s condition,

therapeutic interventions or concomitant drugs; AND occurs immediately following study drug administration, improves upon stopping the drug, or reappears on re-exposure.

10.3 Reporting Adverse Events:

Routine AEs occurring between the start date of intervention until 30 days after the last intervention, or until the event has resolved, the study participant is lost to follow-up, the start of a new treatment, or until the study investigator assesses the event(s) as stable or irreversible, will be reported. New information will be reported after it is received.

- Guidelines for Routine Adverse Event Reporting for Phase 1 Studies
(Regardless of Expectedness)**

Attribution	Grade 1	Grade 2	Grade 3	Grade 4
Unrelated	X	X	X	X
Unlikely	X	X	X	X
Possible	X	X	X	X
Probable	X	X	X	X
Definite	X	X	X	X

- Guidelines for Routine Adverse Event Reporting for Pilot, Phase 2, and Phase 3 Studies (Regardless of Expectedness)**

Attribution	Grade 1	Grade 2	Grade 3	Grade 4
Unrelated			X	X
Unlikely			X	X
Possible	X	X	X	X
Probable	X	X	X	X
Definite	X	X	X	X

10.4 Serious Adverse Events

A serious adverse event (SAE) is any adverse event (experience) that in the opinion of either the investigator or sponsor results in **ANY** of the following:

- Death.
- A life-threatening adverse event (experience). Any AE that places a participant or participants, in the view of the Investigator or sponsor, at immediate risk of death from the reaction as it occurred. It does NOT include an AE that, had it occurred in a more severe form, might have caused death.
- Inpatient hospitalization or prolongation of existing hospitalization (for > 24 hours).

- A persistent or significant incapacity or substantial disruption of the ability to conduct normal life functions.
- A congenital anomaly or birth defect.
- Important Medical Event (IME) that, based upon medical judgment, may jeopardize the participant and may require medical or surgical intervention to prevent one of the outcomes listed above.

10.4.1 Reporting Serious Adverse Events

All new SAEs occurring from the date the participant signs the study consent until 30 days after the last intervention or a new treatment is started, whichever comes first, will be reported. The Roswell Park SAE Source Form is to be completed with all available information, including a brief narrative describing the SAE and any other relevant information.

SAEs occurring after the 30 day follow-up period that the investigator determines to be possibly, probably or definitely related to the study intervention should be reported.

SAEs identified as an Unanticipated Problem by the Investigator must be reported. Please refer to **Section 10.6** for details on reporting Unanticipated Problems.

10.5 Follow-Up for Serious Adverse Events

All related SAEs should be followed to their resolution, until the study participant is lost to follow-up, the start of a new treatment, or until the study investigator assesses the event(s) as stable or irreversible. New information will be reported when it is received.

10.6 Unanticipated Problems

An Unanticipated Problem (UP) is any incident, experience, or outcome that meets all of the following criteria:

- Unexpected (in terms of nature, severity, or frequency) given:
 - a. The research procedures that are described in the study-related documents, including study deviations, as well as issues related to compromise of participant privacy or confidentiality of data.
 - b. The characteristics of the participant population being studied.
- Related or possibly related to participation in the research (possibly related means there is a reasonable possibility that the incident, experience, or outcome may have been caused by the procedures involved in the research).
- Suggests that the research places participants or others at a greater risk of harm (including physical, psychological, economic, or social harm) than was previously known or recognized and if in relation to an AE is also deemed Serious per Section 17.4.

10.6.1 Reporting Unanticipated Problems:

The Reportable New Information (RNI) Form will be submitted to the CRS Compliance Office within 1 business day of becoming aware of the Unanticipated Problem. After review, CRS Compliance will submit the RNI to the IRB.

When becoming aware of new information about an Unanticipated Problem, submit the updated information to CRS Compliance with an updated Reportable New Information Form. The site Investigator or designated research personnel will report all unanticipated problems to the IRB in accordance with their local institutional guidelines.

10.7 Data Safety and Monitoring

If any literature becomes available which suggests that conducting this trial is no longer ethical, the study will be terminated and the IRB will be notified of the new findings. The IRB will be notified of any change in the risk/benefit ratio that would affect whether the study should continue. All serious adverse events will be reported to the IRB according to the established guidelines. A cumulative summary of all adverse events occurring on this study will also be submitted to the IRB at six months review. Toxicity is reported, as required, to the FDA. All study data reviewed and discussed during these meetings will be kept confidential. Any breech in participant confidentiality will be reported to the IRB.

11. Statistical Analysis

Power analysis:

A 2x2 cross-over design with total sample size 100 achieves approximately 80% power to detect 0.5 effect size (the relative magnitude of the effect under the alternative) at significance level 0.05. In other words, assuming the $\text{Log}_2(\text{PSA})$ slope prior to therapy is 0.7 ng/ml/yr. with a standard deviation as 0.7 (based on statistical evaluation of data provided by [name] from his trial of cholecalciferol replacement in men with PSA rising after local therapy.⁵⁵, this design is able detect a 50% reduction of PSA doubling time.⁷¹

Statistical analysis plan:

This is 2 by 2 cross over trial. To address the research objectives, we want to pool information across periods by taking account of the correlation among repeated responses for each individual. The $\text{Log}_2(\text{PSA})$ will be analyzed by linear mixed model in which the fixed effects include treatment (1 for vitamin D3, 2 for control), period (0 for pre study, 1 for first 36 weeks and 2 for second 36 weeks), time (as a continuous variable), time and period interaction, and a variable indicating carry-over effect (1 if the previous treatment assignment is vitamin D3, 2 if the previous treatment assignment is control). The random effect includes random intercept and slope (and a quadratic term if necessary). The significance in the difference between PSA responses for vitamin D3 group and control groups will be assessed by approximate t tests. This will be done using SAS PROC MIXED (SAS 9.1.3., SAS Institute Inc., Cary, NC, USA). The pattern of response of PSA dynamics as well as the absolute change in PSA following vitamin D3 supplementation will be analyzed similarly using the mixed model approach.

In addition to the data analysis described above which analyze $\text{Log}_2(\text{PSA})$, for the men who have 3 or more PSA values from the same laboratory over a period of 18 months or more prior to enrollment, PSA velocity (PSAV) will be calculated and compared to a PSA velocity obtained by analysis of the PSA's during the 2 periods of investigation on the study (the 36 weeks on placebo and the 36 weeks on treatment). Specifically, PSAV can be analyzed as a summary statistics as follows: PSAV will be calculated for the pre-study period, the first 36 week study period, and the second 36 week study period for each participant by simple linear regression. As a preliminary step, summary statistics such as sample mean and standard deviations will be calculated for each group at each period (pre study, first 36 weeks, and second 36 week). Furthermore, the difference in the PSAV caused by vitamin D3 treatment will be tested using two-sample t test comparing the means of differences (first 36 week - second 36 week) in PSAV for the first group (vitamin D3 treatment then control sequence) and the second group (control then vitamin D3 treatment sequence).

The toxicity will be compared as difference in proportion with 95% confidence intervals. Survival would be evaluated on an exploratory basis but no comparison would be made between groups. Relationship between CYP24, 27B1, SNPs and serum 25(OH)D3 vitamin D response to oral D3 supplementation will again be done as an exploratory analysis. We are developing assays to help in this regards and methods for these exploratory analysis would be added as these assays are formulated.

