- Vieth *et al* noted that the rate of rise in PSA is slower during the spring-summer than during the rest of the year, in men who had been followed on an expectant management protocol with selective delayed intervention for clinically localized, low-to-intermediate grade prostate cancer.⁵⁶

These trials demonstrated that the rate of increase in PSA velocity may be altered by high doses of calcitriol. Well tolerated, safe agents are needed that might slow PSA increase. Based on above data, it is rational to study the effect of oral calcitriol supplementation on PSA dynamics in patients with prostate cancer who have chosen expectant management for clinically localized prostate cancer.

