6.0 Study design

Study design

Double-blinded, parallel, placebo controlled randomized 2-group complete cross-over design with 12 week washout period.

Participant Assignment

Eligible patients will be randomly assigned to two groups in 1:1 ratio.

Group A will receive 6,000 IU daily of vitamin D3 (3 capsules of 2000 IU pills).

Group B will receive an identical placebo.

[figure not shown]
Each group will be comprised of approximately 50 patients. Patients who are not able to complete the study will be replaced.

Cross-over will be done after a period of 36 weeks followed by 12 weeks washout period. After 12 week washout period, patients on either arm will be crossed over to receive the drug on the other arm (patients who were on vitamin D arm will get crossed-over to receive placebo, while patients on placebo arm will be crossed-over to receive vitamin D).

They will be stratified randomization based on the Gleason score (less than or equal to 6, OR greater than 6) as well as the season of entry (winter/spring versus summer/fall). Seasonal stratification assignment will be based on the date of randomization:

If randomized between 12/22 and 6/21, it will be considered the winter/spring group and if randomized between 6/22 and 12/21 it will be the summer/fall group.

After completion of study, patient may choose to continue vitamin D if they desire.

Duration of the trial

Patients will be followed for 36 weeks after randomization followed by a washout period of 12 weeks and then be crossed over and followed for an additional 36 weeks (total 84 weeks). 103 patients are expected to enroll over an 11 year period.

Dose Modification:

- 1). If a patient's 25(OH) D3 level reaches > 200ng/ml with 6000 IU or 3 capsules a day, or any \geq grade 3 toxicity possibly related to cholecalciferol develops, 25(OH) D3 or placebo will be discontinued for 4 weeks. Treatment will then be resumed at lower dose of 4000 IU or 2 capsules a day. If a patient misses some period of time off the study drug, the treatment will be resumed such that the patient completes a total of 36 weeks on the study drug.
- 2). If a patient's 25(OH) D3 level reaches > 200ng/ml with the lower dose modification of 4000 IU or 2 capsules a day, or any grade 3 toxicity develops, 25(OH) D3 or placebo will be discontinued for 4 weeks. Treatment will then be resumed at lower dose of 2000 IU or 1 capsule a day.

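### Gleason score and season of entry stratify the randomisation but are not named in the log2(PSA) model or the PSAV comparison; the omission is unbiased, costs little precision and is free to repair

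*Combined protocol and SAP*

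**What the plan says.** Section 6.0 (Participant Assignment) specifies "stratified randomization based on the Gleason score (less than or equal to 6, OR greater than 6) as well as the season of entry". The season stratum is set by the date of randomisation: 22 December to 21 June, or 22 June to 21 December.

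Section 11 gives the log2(PSA) mixed model. Its "fixed effects include treatment (1 for vitamin D3, 2 for control), period (0 for pre study, 1 for first 36 weeks", with period 2 for the second 36 weeks, followed by "time (as a continuous variable), time and period interaction, and a variable indicating carry-over effect". On the random side, "The random effect includes random intercept and slope (and a quadratic term if necessary".

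The supporting velocity analysis "will be tested using two-sample t test comparing the means of differences (first 36 week - second 36 week) in PSAV" between the two sequence groups. No stratum enters that test, and Section 11 describes no stratified or adjusted sensitivity analysis.

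The background links both factors to PSA kinetics. Section 1.3.3 cites a finding that "the rate of rise in PSA is slower during the spring-summer than during the rest of the year". Section 1.2 cites one study relating PSA doubling time to stage and grade, and another in which histologic grade was not important for clinical progression.

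**The concern.** When randomisation is stratified, the usual practice is to carry the strata into the analysis. Doing so makes the model match the allocation, removes any between-man variation that the strata explain, and settles before unblinding a choice that could otherwise be made after seeing the data. Here the sponsor thought both factors worth balancing and the background gives reasons, yet the analysis names neither and does not say why.

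What is at stake is precision and pre-specification, not validity. Balanced strata left out of the model do not bias the treatment estimate. The question is how much of the treatment contrast is between-man, because only that part can gain from adjusting for factors fixed at entry.

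**Working it through.** **1. The plan's own figure.** Section 11 states: "A 2x2 cross-over design with total sample size 100 achieves approximately 80% power to detect 0.5 effect size", "at significance level 0.05". Taken as 50 versus 50, the non-centrality is 0.5 × √(50/2) = 2.5. One-sided power is Φ(2.5 − 1.645) = 0.804, which matches. Two-sided power would be Φ(2.5 − 1.960) = 0.705. The 80% therefore reproduces as a one-sided comparison that takes no credit for the cross-over. I use it below only as a scale.

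**2. Where the omitted factors go.** Write man i's log2(PSA) at time t as fixed effects + (a_i + b_i·t) + e. Gleason stratum and season of entry are constants for each man. A stable effect of either on level is part of a_i, and a stable effect on slope is part of b_i. Both are already absorbed by the random intercept and slope, not by the residual e. Adjusting for strata that explain a share R² of between-man variance replaces the random-effect covariance G by (1 − R²)G and leaves the residual variance σ² unchanged.

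**3. Effect on the standard error (SE).** The treatment SE is the root of the treatment element of [Σ X_i′V_i⁻¹X_i]⁻¹, with V_i = Z_i G Z_i′ + σ²I. It is computed with and without stratum and stratum-by-time columns.

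- From the documents: 100 men, 1:1; follow-up PSA at weeks 12, 24 and 36; second period from week 48 to 84; slope SD 0.7 (taken as between-man, which the plan does not say); fixed effects as listed in Section 11.
- Assumed: intercept SD 1.0; residual SD 0.15 to 0.45; three earlier PSAs at 18, 12 and 6 months before entry; a PSA at week 48; four equal strata; no treatment effect in the pre-study period; carry-over acting only in the second period; R² of 10% or 20%.
- The entry PSA is coded as pre-study, as the schedule in Section 6.1 labels it.

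| Residual SD | SE, unadjusted, carry-over in | Reduction, R² 10% | Reduction, R² 20% | Reduction, carry-over out, R² 20% |
|---|---|---|---|---|
| 0.15 | 0.0361 | 0.14% | 0.32% | 0.01% |
| 0.25 | 0.0589 | 0.37% | 0.82% | 0.03% |
| 0.45 | 0.0992 | 0.91% | 2.00% | 0.10% |

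With the carry-over term the gain is about 0.1% to 2%. Without it the contrast is almost wholly within-man and the gain is 0.1% or less.

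**4. Sensitivity.** If the entry PSA is counted in the first period instead, the range with carry-over becomes 0.3% to 3.5%, and without carry-over it is still at most 0.1%. Section 6.0 keeps men who drop out after the first period in the analysis. If 20% of men have one period only (an assumption), the range in step 3 becomes 0.15% to 2.06%.

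**5. On the plan's power scale.** A 2% smaller SE turns 2.5 into 2.5/0.98 = 2.551, and one-sided power goes from 0.804 to Φ(2.551 − 1.645) = 0.818. In men, that is 100 × (1 − 0.98²) ≈ 4 of 100. At 0.1% nothing visible changes.

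**6. The PSAV comparison.** It uses each man's first-period velocity minus his second-period velocity, so a stable Gleason effect cancels. Season largely cancels too. Period 2 starts 48 weeks after period 1, so the spring-summer share of the two 36-week windows differs within a man by at most about 12 percentage points (mean 7), taking spring-summer as 21 March to 21 September (an assumption).

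**The case against.** The strongest case against raising this is that the design already deals with it. Entry factors cancel in a within-man contrast, the random intercept and slope absorb what remains, and an omitted balanced factor errs on the conservative side. The list of fixed effects is also introduced by a word that does not exclude further terms. And the documents give no effect size for either factor, with mixed evidence on grade, so the 10% to 20% has no source. Nearly all of this stands, and it is why the point is minor. What remains is that no other term is named, that the carry-over term and the single-period men bring in some between-man information, and that the plan neither adjusts nor explains why not.

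Three stronger readings are tempting and not supported:

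- A reader might infer that known slope variation inflates the residual error. Step 2 shows that it sits in the between-man components.
- A reader might quote the larger gain available in a first-period-only comparison. Section 11 contains no such comparison.
- A reader might infer that adding season of entry would model the seasonal effect. Season of entry by time is one fixed linear shift in slope across all of a man's data, whereas season cycles. The entry strata also pool winter with spring, while the cited finding sets spring-summer against the rest of the year.

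**Conclusion.** The point holds as a mismatch between allocation and analysis, with a small cost. Both stratification factors are used in Section 6.0 and neither is named in Section 11. The estimate is unbiased and the SE is at most slightly too large: by roughly 0.1% to 2% with the carry-over term and pre-study PSAs, and by almost nothing without the carry-over term. Those figures rest on the assumed R², intercept SD, residual SD and PSA timing. Coding the entry PSA in the first period would raise the upper end to 3.5% but would not change the conclusion. Nothing here threatens the validity of the treatment test. Severity: minor, a free improvement.

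**What to change.** In Section 11, add the Gleason stratum (6 or below, above 6) and the season-of-entry stratum as fixed effects in the log2(PSA) model, each with its interaction with time. For PSAV, replace the plain two-sample test by a linear model of the within-man difference on sequence group plus the same two factors. If the sponsor prefers the unadjusted analyses, a one-line justification would also close the gap.

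The cost is one sentence, four extra parameters in the mixed model and two in the PSAV model. The data are in hand: Gleason score is recorded at registration (Section 5.1), and the season stratum follows from the randomisation date.

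If the sponsor also wants to account for the seasonal cycle cited in Section 1.3.3, that is a separate addition: calendar season of each PSA as a time-varying covariate.

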1.2 PSA Velocity and Slope

PSA is a useful marker to identify progressive disease in patients with prostate cancer.¹² Studies have shown that serum PSA levels correlate with tumor volume and pathologic stage.^{13 14 15} In addition, a rapid PSA change (expressed as PSA velocity [PSAV] or PSA doubling time [PSADT]) was shown to correlate with the presence of cancer and metastatic disease. PSAV is defined as rate of change in PSA over a predefined period of time.¹⁶ PSA dynamics provides an insight into the biological behavior of the tumor and tumor kinetics. There is recent evidence to suggest that PSA dynamics is not only useful in prostate cancer detection but also in predicting treatment outcomes. Schmid et al. studied serial measurements of PSA in men during at least 1 year of expectant management, and they found that PSADT was related to tumor stage and grade.¹⁷ McLaren et al. found that PSADT was the most powerful indicator of clinical progression in 113 men observed expectantly; whereas, T classification, histologic grade, and initial levels of PSA were not important.¹⁸ D'Amico et al reported that a PSAV greater than 2 ng/ml per year was associated with greater prostate cancer-specific mortality following radical prostatectomy and external beam radiation therapy.^{19 20}

PSA slope is defined as the slope of the linear line of \log_2 (PSA) versus time. The advantage to this transformation is the inverse of the slope is the time to doubling the PSA value.^{21 22} Following PSA dynamics can help guide treatment strategy in patients who choose expectant management.

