2.0 Primary Objective

- 1) To determine the PSA response with oral high dose vitamin D3 supplementation in patients with localized, histologically proven adenocarcinoma of the prostate who have not received any treatment for prostate cancer ever and have chosen expectant management.

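### The log2(PSA) mixed model has no treatment-by-time term, so no coefficient estimates the slope difference on which the trial is powered

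*Combined protocol and SAP*

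**What the plan says.** The power paragraph in Section 11 takes a log2(PSA) "slope prior to therapy is 0.7 ng/ml/yr. with a standard deviation as 0.7", gives an effect size of 0.5 with about 80% power for 100 men, and concludes that "this design is able detect a 50% reduction of PSA doubling time". Section 1.2 defines PSA slope on the log2 scale because "the inverse of the slope is the time to doubling the PSA value". Section 6.1 defends the 36-week period on the ground that a change in PSA slope can be seen over it.

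The analysis paragraph that follows lists treatment, period (0, 1, 2), "time (as a continuous variable), time and period interaction, and a variable indicating carry-over effect", with a random intercept and slope per man. Carry-over is coded "1 if the previous treatment assignment is vitamin D3, 2 if the previous treatment assignment is control". On the test it says: "The significance in the difference between PSA responses for vitamin D3 group and control groups will be assessed by approximate t tests". For the secondary objectives, "The pattern of response of PSA dynamics as well as the absolute change in PSA following vitamin D3 supplementation will be analyzed similarly". The primary objective in Section 2.0 is "To determine the PSA response with oral high dose vitamin D3 supplementation", with no scale or contrast named.

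Section 11 then adds a comparison of PSA velocity between the two sequences by two-sample t test. It is introduced for men with enough earlier PSA values.

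**The concern.** The planning quantity is a slope, but the listed model gives treatment only a level. The time-by-period term cannot stand in for the missing one, because each active period contains men on both treatments. The random slope belongs to the man and not to the treatment. Carry-over is a second level shift, for the previous treatment.

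A significant result from the main model would therefore show that log2(PSA) was lower on vitamin D3. It would not show whether PSA was rising more slowly, and so whether doubling time had changed. That is the statement the power paragraph leads a reader to expect.

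**Working it through.** **1. The plan's 80%.** Effect size 0.5 × SD 0.7 = 0.35 per year. For two independent groups of 50, the standard error is 0.7 × √(2/50) = 0.14, and 0.35/0.14 = 2.5. One-sided 0.05: Φ(2.5 − 1.645) = 80.4%. Two-sided: Φ(2.5 − 1.96) = 70.5%. The plan does not state sidedness. The stated power is reproduced, one-sided, as a comparison of slopes, so slope is the powered quantity.

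**2. Doubling time.** This is 12/slope in months, by Section 1.2 (the slope is taken as log2 per year, although the plan prints ng/ml/yr).
- Slope 0.70: 17.1 months.
- Slope 0.35 (effect size 0.5): 34.3 months, which is doubled.
- Doubling time cut by 50%: 8.6 months, so slope 1.4, a difference of 0.7 and effect size 1.0, with PSA rising faster.

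The wording and the effect size disagree.

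**3. Two different truths in the listed model.** On-treatment PSAs are at weeks 12, 24 and 36, on average 24 weeks or 0.460 years. A slope fall of 0.35 per year lowers log2(PSA) by 0.35 × 0.460 = 0.161 on average, and by 0.35 × 0.690 = 0.24 at week 36. The comparison case is a one-off drop of 0.161, complete by week 12, with slope unchanged.

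Expected coefficients come from generalised least squares.
- From the plan: 50 men per sequence, slopes 0.70 and 0.35, slope SD 0.7, visits every 12 weeks.
- Assumed: intercept SD 1, pre-study PSAs at 18, 12 and 6 months before entry, residual SD 0.25 on the log2 scale, immediate slope effect, and period 0 coded as untreated with no carry-over in periods 0 and 1.

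The plan leaves open whether week 0 belongs to period 0 or 1, whether a week-48 PSA is taken, and whether these values carry the code of their period or count as untreated.

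| Week 0 in | Week-48 PSA | Coded by period: slope fall / drop | Coded untreated: slope fall / drop |
|---|---|---|---|
| period 0 | yes | −0.20 / −0.20 | −0.138 / −0.161 |
| period 0 | no | −0.16 / −0.16 | −0.161 / −0.161 |
| period 1 | yes | −0.12 / −0.12 | −0.120 / −0.161 |
| period 1 | no | −0.05 / −0.05 | −0.112 / −0.161 |

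Coded by period, the two truths coincide in every row. Coded as untreated, they differ in three rows of four, but one coefficient still cannot say which truth produced it.

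**4. Adding treatment by within-period time.**
- Coded by period, the one-off drop is read as a slope of −0.14, 0.00, −0.21 and −0.14 per year (rows in order), so the term alone is not enough.
- Coded as untreated, the slope fall gives −0.350 per year with level 0.000, and the drop gives 0.000 per year with level −0.161, in all four rows.

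**5. Limit of that separation.** Suppose the drop is half complete at week 12 and complete at week 24: −0.0805, −0.161, −0.161. The fitted slope is −0.0805/(24 weeks = 0.460 years) = −0.175 per year in all four rows, with p<0.05 in 36–49% of trials at residual SD 0.25.

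**6. Illustrative power** for the slope fall with untreated coding, two-sided 0.05.
- Slope test: 95, 90, 97, 94% at residual SD 0.25, and 73, 63, 79, 72% at 0.35.
- Listed level test: 60–98% at 0.25.
- Slope test with a modelled patient-by-period slope SD of 0.35 (0.5): 83–92% (77–86%) at 0.25.
- If that variation exists but is ignored: type I error 7–9% (10–12%).

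**The case against.** The strongest reply is that the documents never name the log2 slope as the primary endpoint. The objective speaks only of PSA response, PSA dynamics sits among the secondary objectives, and the list of fixed effects is introduced by a word that need not be exhaustive. The first part stands: a level estimand is a possible reading. But no power is given for a level effect, so that reading also needs a change. As for the list, it goes down to the carry-over codes, and no other section supplies the missing term.

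Second, the PSA velocity t test does compare slopes between sequences. It mitigates the problem in part, but it is supplementary, is introduced for a subset, and works on PSA velocity and not on log2(PSA).

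Third, a reader might infer that the main analysis would miss a slope effect. The documents do not support that: the level coefficient picks up a slope fall as a mean shift, and its power can be adequate. A reader might also infer that the two truths are indistinguishable under every coding, or that the interaction alone would prove a change in doubling time. Steps 3 to 5 show that neither holds. Gradual onset is plausible on the protocol's own account: Section 1.4 says serum vitamin D takes at least three months to reach steady state.

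**Conclusion.** The concern holds as a mismatch between the listed analysis and the powered quantity: a slope difference of 0.35 per year is powered, and no listed coefficient estimates it. It is not shown that the wrong hypothesis would be tested, because the objective leaves the estimand open, nor that power would be lost. The equal coefficients in step 3 require coding by period and a drop complete by week 12. The clean separation in step 4 requires untreated coding, immediate onset of the slope effect and, again, a drop complete by week 12. The power and error-rate figures in step 6 are illustrative, because residual SD, intercept SD and the timing of pre-study PSAs are not in the documents. The contradiction over doubling time is plain arithmetic and needs no assumption beyond Section 1.2. This should be fixed before the analysis, and it is inexpensive to fix.

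**What to change.** Amend Section 11 before unblinding.

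- **(a) Estimand.** Add treatment by within-period time, keep the other listed terms including carry-over, and name the interaction (difference in log2(PSA) slope per year, vitamin D3 minus control) as the test that matches the power statement. If a level effect is the intended primary, say so and re-derive the power for it.
- **(b) Coding.** Code the week-0 PSA, and a week-48 PSA if one is taken, as untreated start-of-period values. State the treatment code for period 0 and the carry-over codes for periods 0 and 1. State also that this separates a drop from a slope change only if the drop is complete by week 12, and report the level difference at a named week beside the slope. At week 36 that would be −0.24 for the slope fall and −0.16 for the drop.
- **(c) Variance.** Include a patient-by-period random slope, or robust standard errors, for the slope test.
- **(d) Wording.** Reconcile the doubling-time sentence with effect size 0.5, which corresponds to a halved slope and a doubled doubling time.

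The cost is SAP text and one changed PROC MIXED model, with no new patients or data. Item (c) gives up some power: 77–92% against 90–97% at residual SD 0.25, under the assumptions above.
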